7.5.3. Abnormal laboratory examination

Laboratory test results will be recorded on the laboratory test data page of the CRF. The study monitor will continuously review the CRF records. Any laboratory test abnormalities that meet the SAE criteria should be immediately reported using the SAE report form and also recorded as an AE in the CRF.

Laboratory abnormalities do not need to be reported as AE on the AE page of the CRF unless they meet any of the following criteria:

- Accompanied by clinical symptoms;
- Changes in study medication are required (e.g., dose adjustment, temporary interruption or permanent discontinuation of administration)
- Changes in concomitant therapy are required (e.g., add corresponding therapy, discontinue concomitant therapy or administration, discontinue or make other changes);
- The researchers considered it of important medical significance (the researchers decided whether the independent laboratory test abnormalities could be classified as AE based on scientific medical judgment).

7.6 Follow-up and reporting of adverse events

7.6.1 Collection and follow-up of adverse events/severe adverse events:

The collection period of adverse events starts from the date of signing the informed consent form by the subject and ends 30 days after the last study drug.

The collection period of serious adverse events begins with the signing of informed consent by the subject. For serious adverse events unrelated to the study drug, the collection period is 90 days after the last study drug or the start of new anti-tumor treatment (whichever comes first); after that, only serious adverse events related to the study drug will be collected.

Follow-up for adverse events or serious adverse events should continue until the event resolves, is alleviated to baseline levels or ≤ 1 level, reaches a stable state, or is reasonably explained (such as loss to follow-up or death). The best possible outcome should be sought. Researchers should inquire about any adverse events or serious adverse events that have occurred since the last visit during each follow-up visit and provide timely follow-up information as requested by the sponsor.

7.6.2 Reporting of serious adverse events:

During the study, regardless of the treatment received by the patient, any serious adverse events or serious laboratory test results that occur must be reported by the investigator to the CFDA Serious Adverse Event Report Form

and the adverse event report form, and reported to the designated contact within 24 hours of learning:

Contact person for serious adverse event reporting: GCP Office, Sixth Affiliated Hospital of Sun Yat-sen University

Contact person of the research group leader: [name] (The Sixth Affiliated Hospital of Sun Yat-sen University)

Email: [contact]

Address: [name]

The contact person for serious adverse event reporting should, within one working day of receiving a report from a researcher, fax the signed form to the lead unit. The report must adhere to the guidelines and standards set by the International Council for Harmonization (ICH) for the management of safety data in clinical trials and the definition of rapid reporting.

7.6.3 Reporting of non-serious adverse events:

In addition to specific adverse events, other non-serious adverse events should also be recorded by researchers on the adverse event page of the CRF in a retrieval format. The collection period for adverse events of each patient is from the date of signing the informed consent form to 30 days after the last medication administration. The minimum requirements for recording on the adverse event report form include: the subject's identity, the drug, the duration of the adverse event, the start date of the event, and the causality.

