4.1 Study treatment grouping

This study is a prospective, open-label, double-arm, Phase II clinical trial that includes a neoadjuvant treatment group using the mFOLFOX6 regimen and a neoadjuvant treatment group combining the mFOLFOX6 regimen with Citrus Flavonoid Tablets (Aimalang). The study aims to enroll patients with locally advanced rectal cancer who are in clinical stage I, II, or III. Endoscopic biopsy specimens will be collected for YWHAB immunohistochemical testing to identify patients with high YWHAB expression in locally advanced rectal cancer. These patients will then be randomly assigned to either the mFOLFOX6 treatment group or the mFOLFOX6 combined with Citrus Flavonoid Tablets (Aimalang) treatment group for neoadjuvant therapy. The mFOLFOX6 regimen involves 4-6 cycles before surgery and 6-8 cycles after surgery, with each cycle lasting 14 days: on day 1, 85 mg/m² of oxaliplatin is administered intravenously over 180 minutes; on day 1, 400 mg/m² of leucovorin is administered intravenously over 120 minutes; and on day 1, 2400 mg/m² of 5-fluorouracil is administered continuously intravenously for 46 hours. The Citrus Flavonoid Tablets (Aimalang) treatment regimen involves taking 500mg of Citrus Flavonoid Tablets (Aimalang) orally three times daily, with doses given on days 1-14 of each 14-day cycle.

This trial allows for dose adjustments. Patients who experience disease progression during neoadjuvant therapy may stop the study treatment and directly undergo surgery or follow local guidelines. If a patient cannot tolerate the planned 6 cycles of neoadjuvant therapy, early surgery can be considered. Any patient who has received another anticancer regimen before surgery will stop the study treatment and be managed according to local guidelines. The postoperative

treatment for both groups is determined by the investigator, which may include continuing the mFOLFOX6 regimen combined with Citrus Flavonoid Tablets (Aimalang). It is important to note that all patients in the control group are prohibited from taking Citrus Flavonoid Tablets (Aimalang) without authorization during the trial. If a patient needs to take this medication for any reason, they should consult their primary physician, who will decide whether to use an alternative or discontinue the patient's participation in the trial.

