4.2.3 Study drug dose levels

If a reduction in drug dosage is required in medical practice, the dose levels of oxaliplatin and 5-fluorouracil can be adjusted according to the criteria listed in Table 1.2. Each adjustment should only reduce one dose level, and the total number of dose level adjustments throughout the study period should not exceed two. The fixed dose of suberythrocitin is 400 mg/m² or 7.5 mg/kg (for the 3-week regimen). All dose level adjustments must be clearly documented with the reasons for the adjustment.

Table 1.2 Study drug dose levels

Name of drug	Initial dose (mg/m ²)	Dose level-1 (mg/m ²)	Dose level-2 (mg/m ²)
oxaliplatin	85	65	50
5-FU	2400	2300	2200
Citrus flavonoid tablets (Aimalang)	Take orally, 500mg Tid	Take orally, 500mg twice daily	Take orally, 500mg Qd

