8.4 Safety analysis and statistical methods

The security analysis will be based on the security set. The security analysis is limited to descriptive statistical summaries, including but not limited to the following aspects, which will be described in the statistical analysis plan:

- Summary of adverse events (all-cause and treatment-related);
- Incidence and severity of adverse events (all-cause and treatment-related);
- Summary of details of serious adverse events;
- Analysis of adverse event correlation;
- Abnormal occurrence of laboratory indicators, vital signs and electrocardiogram data.

The security analysis will be based on descriptive statistical summaries and based on the security set.

This study will use the standard medical terminology set (MedDRA) of pharmaceutical management to code adverse events. The study will use tables to list all adverse events, drug-related adverse events, serious adverse events, and drug-related serious adverse events that occurred during treatment, according to the NCI CTCAE version 6.0 standard and using the worst grading. Additionally, the study will summarize the laboratory test parameters during the research period according to the NCI CTCAE version 6.0 standard and using the worst grading.

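### Adverse event collection is timed from the last study drug, so after the same last chemotherapy cycle it can run up to about 11 days longer in the tablet arm than in the control arm

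*Combined protocol and SAP*

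**What the plan says.** Section 7.6.1 starts adverse event collection at consent and says that it "ends 30 days after the last study drug". Section 7.6.3, on non-serious events, words the period as running "from the date of signing the informed consent form to 30 days after the last medication administration". For serious adverse events (SAEs) unrelated to study drug, 7.6.1 sets the limit at 90 days after the last study drug, or at the start of new anti-tumor treatment if that comes first. Related SAEs go on being collected, with no stated end. One rule serves both arms.

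The dose table in section 4.2.3, "Table 1.2 Study drug dose levels", covers oxaliplatin, 5-FU and the tablets, so all three count as study drug. Under section 4.1 the chemotherapy starts on day 1, and its longest component, 5-FU, is "administered continuously intravenously for 46 hours". The tablets follow a different calendar, with "doses given on days 1-14 of each 14-day cycle". The plan is 4 to 6 cycles before surgery and 6 to 8 after. Section 4.1 leaves postoperative treatment in both groups to the investigator, who may continue the tablet combination. Control patients may not take the tablets without authorization.

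Section 8.4 limits safety analysis to descriptive summaries. Its tables run from all adverse events to "drug-related serious adverse events that occurred during treatment". It does not define the treatment period and does not refer to the collection window in 7.6.

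**The concern.** The clock starts at an event whose timing depends on the arm. Two patients who receive the same last cycle of chemotherapy can be followed for different lengths of calendar time, only because one of them takes tablets until the end of the cycle. Events in the extra days can then be counted in one arm and not in the other, even if the tablets add no toxicity.

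The rate of treatment-related reactions of grade III or above is a secondary endpoint (section 2.3). The trial is open-label, safety is reported descriptively, and section 8.4 plans no exposure-adjusted rates. Readers will therefore compare raw percentages between the arms.

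**Working it through.** The plan states no figure for this point, so there is none to reproduce. The check is calendar arithmetic.

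**Inputs**
- Last study drug in a cycle of mFOLFOX6 alone: 46 hours of 5-FU from day 1 (section 4.1). With an assumed start between 08:00 and 12:00, and 0 to 5 hours of earlier infusions, it ends on day 3 in every case.
- Last study drug in a cycle with tablets: day 14 (section 4.1).
- Windows: 30 days for adverse events, 90 days for unrelated SAEs (section 7.6.1).
- Cycle length: 14 days (section 4.1).

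**Closing day, counted from day 1 of the last cycle**

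| Window | mFOLFOX6 alone | With tablets | Gap |
|---|---|---|---|
| Adverse events | 3 + 30 = 33 | 14 + 30 = 44 | 11 |
| Unrelated SAEs, if no new anti-tumor treatment | 3 + 90 = 93 | 14 + 90 = 104 | 11 |

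If the last administration in 7.6.3 is read as the start of the infusion on day 1, the gap is 14 − 1 = 13 days.

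**When the gap arises**
- Study treatment ends in the neoadjuvant phase, with tablets through day 14 in the tablet arm: 11 days.
- Tablets continue after surgery in the tablet arm only: 11 days.
- The final cycle is mFOLFOX6 alone in both arms, or includes tablets in both: 0 days.

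If no control patient takes tablets, the average gap between arms is 11 × p, where p is the share of tablet-arm patients whose last cycle includes tablets through day 14. The documents do not give p. Over its range from 0 to 1 the average gap runs from 0 to 11 days; at p = 0.5 it would be 5.5.

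**Size relative to time from first dose.** For k cycles, leaving out the interval for surgery, the control time is 14(k − 1) + 3 + 30 and the tablet time is 14(k − 1) + 14 + 30.

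| Cycles k | Control, days | Tablet, days | 11 / control |
|---|---|---|---|
| 4 | 75 | 86 | 14.7% |
| 6 | 103 | 114 | 10.7% |
| 10 | 159 | 170 | 6.9% |
| 12 | 187 | 198 | 5.9% |
| 14 | 215 | 226 | 5.1% |

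The first two rows apply only if study treatment stops before surgery. The planned course is 4 + 6 = 10 to 6 + 8 = 14 cycles. Collection opens at consent, and the surgical interval adds further days, so the true percentages are somewhat lower.

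**Which events can differ.** Non-serious events starting on about days 34 to 44 of the last cycle, and unrelated SAEs starting on about days 94 to 104. Related SAEs are collected without an end date, so this rule does not cut them off.

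**The case against.** The strongest defence is that every patient gets the same 30 days after last exposure, which is a reasonable safety rule. That is true, and the fix should keep it. It does not make the arms comparable, because after the same chemotherapy the calendar time still differs.

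Four stronger readings are tempting, and the documents do not support them.

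- **That every tablet-arm patient is followed 11 days longer.** The last planned cycle is postoperative, and section 4.1 does not fix by arm whether it includes tablets. The gap can be zero.
- **That the tablet arm's rate is inflated.** This is possible but not shown. Within the grade III or above endpoint, only non-serious related events that start in the extra days are affected. The documents give no basis for estimating how many there would be.
- **That operative complications are captured in one arm only.** The plan gives no surgery date. Suppose surgery on day 35 of the last cycle and no postoperative study drug. The 30-day window then covers 0 days after surgery in controls and 44 − 35 = 9 in the tablet arm, but for non-serious events only. Complications that prolong a hospital stay are SAEs under section 7.3. Unrelated SAEs would be covered for 93 − 35 = 58 and 104 − 35 = 69 days, if no new anti-tumor treatment starts. If postoperative study cycles are given as planned, collection runs through surgery in both arms.
- **That section 8.4 counts days 4 to 14 of the last cycle as on treatment in one arm only.** Section 5.2 ends the treatment period when study treatment is discontinued, which allows that reading. But a cycle lasts 14 days in both arms, so treatment can equally be read as lasting to the end of the cycle. The term is undefined, and events on those days are collected in both arms in any case.

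**Conclusion.** The point holds as a conditional one. The anchor in sections 7.6.1 and 7.6.3 depends on the arm, and it can keep the tablet arm under observation up to about 11 days longer after identical chemotherapy (13 if the clock runs from the start of the infusion). The range is 0 to about 11 days, depending on whether the last cycle includes tablets. The bar on unauthorized tablets in controls makes a gap in the tablet arm's direction the more likely one.

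The likely consequence is modest: some extra non-serious events, including non-serious treatment-related events of grade III or above, and some extra unrelated SAEs in the tablet arm. The primary endpoint is untouched. The calculation assumes that tablets are taken through day 14 of the last cycle, that 5-FU ends on day 3, and that no new anti-tumor treatment closes the 90-day window first. This is a cheap improvement to the plan and not a flaw that threatens its conclusions.

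**What to change.** - **Sections 7.6.1 and 7.6.3:** run the 30-day and 90-day windows, in both arms, from day 14 of the last mFOLFOX6 cycle started, or from the last study drug dose if that is later. Use the same words in both sections, and keep the existing cut-off at new anti-tumor treatment for unrelated SAEs.
- **Section 8.4:** tabulate events from first dose to the end of that window, in place of the undefined reference to treatment.

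The provision for a later last dose is needed because section 4.2.1 allows a delay of up to 14 days and does not say whether tablets stop meanwhile. Without it, a patient who takes tablets past day 14 would have fewer than 30 days of collection after the last one. With it, a small difference between arms can remain for such patients.

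The cost is a wording change in three places and up to about 11 more days of event collection per control patient, with no new visit or test. Dosing and clinical management do not change.

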 - Routine urine: white blood cells, red blood cells, protein in urine; if protein in urine is greater than or equal to 2+, 24-hour urine protein quantification should be added;
 - Blood biochemical: ALT, AST, γ -GT, TBIL, DBIL, AKP, BUN or urea (preferably BUN), TP, ALB, Cr, GLU, K+, Na+, Ca2+, Mg2+, Cl-;

- Tumor markers;
- Coagulation function: activated partial thromboplastin time (APTT), prothrombin time (PT), thrombin time (TT), fibrinogen (FIB), international normalized ratio (INR);
- 12. Lead electrocardiogram: attention should be paid to QT, QTc and P-R intervals. If there are abnormalities, other relevant tests should be done according to the investigator's judgment;
- Echocardiography: at least the assessment of left ventricular ejection fraction (LVEF) should be included;
- Pregnancy test: suitable for women of childbearing age, using serum pregnancy test.

5.2, treatment period

The treatment period begins with the first dose of the study drug and ends when the study treatment is discontinued. The first study medication should be administered as close as possible to the completion of the screening period to confirm eligibility. All examinations and assessments, except for imaging studies, should be completed within three days before the first dose. For the laboratory tests (complete blood count, urinalysis, fecal occult blood test, biochemical blood tests, coagulation function, and thyroid function) and electrocardiogram on the first day of the first cycle, if baseline laboratory tests were conducted within seven days before the first dose, they do not need to be repeated.

The following assessments should be completed prior to each study treatment administration:

- Weight and ECOG score;
- vital sign ;
- check-up ;
- Complete blood count: red blood cell count, hemoglobin, platelet count, white blood cell count, neutrophil count and lymphocyte classification

count;

- Blood biochemical: ALT, AST, γ -GT, TBIL, DBIL, AKP, BUN or urea (preferably BUN), TP, ALB, Cr, GLU, K+, Na+, Ca2+, Mg2+, Cl-;
- Routine urine: white blood cells, red blood cells, protein in urine; if protein in urine is greater than or equal to 2+, 24-hour urine protein quantification should be added;
- Coagulation function: activated partial thromboplastin time (APTT), prothrombin time (PT), thrombin time (TT), fibrinogen (FIB), international normalized ratio (INR);
- Tumor markers;

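### AE collection is timed from the last study drug and not from surgery, so operated patients who receive no postoperative study drug have little or no postoperative collection of non-serious AEs

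*Combined protocol and SAP*

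**What the plan says.** **AE window.** Section 7.6.1 starts collection at consent and says that it "ends 30 days after the last study drug". Section 7.6.3 gives the period for non-serious AEs as "from the date of signing the informed consent form to 30 days after the last medication administration". The wording differs (study drug in one, medication in the other), but both stop at 30 days and neither refers to surgery.

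**Postoperative treatment.** Section 4.1 plans it: "The mFOLFOX6 regimen involves 4-6 cycles before surgery and 6-8 cycles after surgery". The same section then says that postoperative "treatment for both groups is determined by the investigator", with continuation given as one possibility. Patients who progress during neoadjuvant therapy "may stop the study treatment and directly undergo surgery". In addition, "Any patient who has received another anticancer regimen before surgery will stop the study treatment". So the protocol foresees patients who are operated on and have no study drug afterwards. It does not say how many.

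**Serious AEs (SAEs).** Under 7.6.1, unrelated SAEs are collected for 90 days after the last study drug, or until new anti-tumor treatment starts if that is sooner. Related SAEs have no end date. Section 7.3 counts prolonged hospital stay and medically significant events as serious.

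**Other contacts.** The treatment period in 5.2 "ends when the study treatment is discontinued". The exit visit in 5.3 documents AEs but has no fixed day and no link to surgery. Contacts under 5.4 are three-monthly and are described as collecting survival and later anti-tumor treatment. Section 7.6.1 also asks investigators to enquire about AEs at each follow-up visit.

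**Reporting.** Section 8.4 promises an all-cause and treatment-related summary of AE incidence and severity. Its AE tables are limited to events during treatment.

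**The concern.** Resection is part of the plan for every patient, yet the AE clock takes no account of it. If study drug restarts after surgery, the window runs through the operation without a break. If it does not, the window runs from the last preoperative dose and may close before the operation or soon after it.

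Whether a patient's non-serious postoperative events are recorded therefore depends on a later treatment decision, taken in an open-label trial. A complication may itself be the reason that chemotherapy is not resumed, so collection can depend on outcome. An all-cause summary would then mix patients with full, partial and no postoperative collection, and a reader could not tell which were which. Events not recorded at the time are hard to recover reliably afterwards.

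**Working it through.** The plan states no figure to reproduce here. The check is date arithmetic, per patient.

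**Inputs from the documents**
- AE window: 30 days after last study drug (7.6.1, 7.6.3).
- Unrelated SAE window: 90 days after last study drug, absent new anti-tumor treatment (7.6.1).
- Study drugs: oxaliplatin, 5-FU and the tablets (Table 1.2).
- Last drug in a cycle: the 46-hour 5-FU infusion ends on about day 3; tablets have "doses given on days 1-14 of each 14-day cycle" (4.1).

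**Assumed, because not given:** the interval to surgery.

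**1. Postoperative cover by gap.** With g = days from last study drug to surgery and no postoperative study drug:

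non-serious AE days = max(0, 30 − g); unrelated SAE days = max(0, 90 − g)

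| g (days) | Non-serious AEs | Unrelated SAEs |
|---|---|---|
| 7 | 23 | 83 |
| 14 | 16 | 76 |
| 21 | 9 | 69 |
| 28 | 2 | 62 |
| 30 | 0 | 60 |
| 42 | 0 | 48 |
| 56 | 0 | 34 |

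Unrelated SAEs keep at least 30 postoperative days at every gap shown. Non-serious AEs do not.

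**2. Could the arms differ?** Take day 1 as the start of the last neoadjuvant cycle. The AE window closes on day 3 + 30 = 33 in the control arm. In the tablet arm it closes on day 14 + 30 = 44 if tablets run to day 14, or on day 7 + 30 = 37 if they stop on day 7. Surgery 2, 4, 6 or 8 weeks after day 1 falls on day 15, 29, 43 or 57. Cover is closing day minus surgery day, floored at 0:

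| Surgery day | Control | Tablets to day 14 | Tablets to day 7 |
|---|---|---|---|
| 15 | 33 − 15 = 18 | 44 − 15 = 29 | 37 − 15 = 22 |
| 29 | 33 − 29 = 4 | 44 − 29 = 15 | 37 − 29 = 8 |
| 43 | 0 | 44 − 43 = 1 | 0 |
| 57 | 0 | 0 | 0 |

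If tablets stop on day 3, both windows close on day 33 and there is no difference. If surgery is timed from each arm's own last dose, both arms have 16, 2, 0 and 0 days at 2, 4, 6 and 8 weeks. The gap between arms therefore ranges from 0 to 11 days. It needs surgery timed from cycle start and tablets continued beyond the infusion.

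**3. SAE cover on the same calendar.** The unrelated SAE window closes on day 3 + 90 = 93 (control) or 14 + 90 = 104 (tablets to day 14). Thirty full postoperative days need surgery by day 63 or day 74. Surgery on day 57 meets both.

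**4. Do the other contacts fill the gap?** The exit visit is triggered by completing treatment or leaving the study, so it may precede surgery. The duty to enquire at follow-up visits does not change an end date that the protocol states twice, and the three-monthly contacts have another stated purpose. These provisions reduce the practical loss but do not extend the window.

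**The case against.** The strongest reply is that this is a drug trial with a drug-safety endpoint. The only safety endpoint in 2.3 is the rate of treatment-related reactions of grade III or above; no objective concerns surgical morbidity, and 30 days after last exposure suits that purpose. The plan is that patients receive 6-8 postoperative cycles, and those who do are covered. A complication bad enough to prevent chemotherapy would often be serious under 7.3 and so be collected for longer. The AE tables in 8.4 are limited to events during treatment, so in these patients postoperative events would not appear even if recorded. Section 8.4 leaves the detail of its all-cause summary to the statistical analysis plan, and the text at hand does not fix that summary's event window.

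Most of this stands, and it sets the limits of the point. What remains is narrow: non-serious events, in patients operated on without later study drug, in the all-cause summary.

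A reader might infer more, and the documents do not support it:
- *That serious surgical complications are lost.* At the gaps examined, unrelated SAEs are covered for at least 30 postoperative days unless new anti-tumor treatment starts, and related SAEs have no end date.
- *That the rule biases the comparison towards one arm.* The difference depends on how surgery is timed and when tablets stop, and it can be zero.
- *That 7.6.1 and 7.6.2 contradict each other on SAEs after new anti-tumor treatment.* Section 7.6.2 sets the form, contact and deadline for reporting. Its remark that reporting does not depend on the treatment received can be read as referring to study arm. The two sections can be read together.

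**Conclusion.** The point holds in limited form, at minor severity. As written, the rule gives an operated patient with no postoperative study drug max(0, 30 − g) postoperative days of non-serious AE collection, and none once the gap reaches 30 days.

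The effect is confined to the descriptive all-cause AE summary in 8.4. The primary endpoint (ypTNM 0-I) does not use these data. The treatment-related grade III+ rate is little affected. The direction of any difference between arms is unknown.

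The per-patient figures rest on assumed surgery intervals, on the infusion ending on about day 3, and on reading the medication in 7.6.3 as study drug. The trial-level effect cannot be sized, because the documents give neither the interval to surgery nor the number of patients who do not resume.

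**What to change.** 1. In 7.6.1 and 7.6.3, end AE collection at the later of 30 days after the last study drug and 30 days after surgery, in both arms, and use the same term for the drug in both places. Every operated patient then has the same 30-day minimum, whatever g is.
2. In 8.4, state that AEs in the 30 days after surgery are summarised by arm. Without this, the tables limited to events during treatment would not show the added events.
3. Optionally, apply the same 30-day postoperative minimum to unrelated SAEs when new anti-tumor treatment has started.

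The cost is a sentence in each of the three sections, a few more AE entries, and a chart review or telephone contact at about postoperative day 30 for patients who do not resume study drug. No such contact is scheduled now.
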